4.3 Premature Subject Termination from the Study

4.3.1 Criteria

No subject initiating therapy in this trial will be replaced.

Any subject may be prematurely terminated from additional allergen exposures, but maintained on longitudinal follow-up for the following reasons:

• Anaphylaxis resulting in hypotension, neurological compromise or mechanical ventilation secondary to Baked Egg or Egg OIT dosing or any egg food challenge.

Any subject deemed to have severe symptoms and receives aggressive therapy at any time should be discontinued from further therapy, including the following:

- Poor control or persistent activation of secondary atopic disease (e.g., AD, asthma).
- Started on ARBs, ACE inhibitors, beta-blockers, or other prohibited meds and there are no alternative meds available per the prescribing doctor, they will be removed from further treatment.
- Pregnancy.
- Egg OIT Group subjects:
 - Circumstances (e.g., concurrent illness, such as gastroenteritis) requiring missed Egg OIT maintenance dosing of >7 consecutive days (this does not include subjects intentionally removed from therapy to administer an OFC off therapy).
 - Non-adherence with home Egg OIT dosing protocol (excessive missed days; i.e., >3 consecutive days missed on 3 occasions), would be a safety issue warranting discontinuation.

Any subject may be prematurely terminated from the study if:

- The subject elects to withdraw consent from all future study activities, including followup.
- The subject is "lost to follow-up" (i.e., no further follow-up is possible because attempts to reestablish contact with the subject have failed).
- The subject has biopsy documented Eosinophilic Esophagitis (EoE).

• The subject dies.

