If a subject fails dose escalation after three consecutive (with 2-4 weeks between) attempts, he/she will be considered a dose escalation failure and the last tolerated dose will be accepted as the maintenance dose. For a completed dose escalation with no symptoms, subjects should be observed for 30 minutes. For mild symptoms, subjects should have a 1-2 hours post-protocol observation period. For moderate to severe symptoms, the observation period should be at least 4 hours and up to 24 hours based on symptoms and treatment regimen needed to stabilize the subject.

Any subject deemed to have severe symptoms including hypoxia, hypotension or change in mental status (stage 3 defined in Appendix 3) and receives aggressive therapy at any time should be discussed with the Study Chair or Co-Chair and discontinued from active therapy.

For specific questions related to dosing escalation or continuation of the same dose that are not answered in the above protocol, the Study Chair or Co-Chair will be available for questions and decision-making.

Any subject who discontinues build-up dosing due to repeated allergic reactions to the egg product will have his/her mechanistic blood drawn within approximately 1 week of discontinuation of therapy.

6.4.2 Treatment for reactions during the Build-Up and Maintenance Phases

Treatment of individual reactions should be with either an antihistamine and/or epinephrine, along with IV fluids, albuterol, and steroids as indicated. Generally, for mild and moderate symptoms, the subject should receive antihistamines, and for more severe symptoms, the subjects should receive epinephrine, antihistamines, and then the other medications as indicated. If severe anaphylaxis (stage 3 defined in Appendix 3) occurs at any time, dose escalation will stop and the dose will be reduced to the last tolerated dose (must be at least 350 mg egg white solid) and the subject continued on that dose as long-term maintenance without further escalation.

Antihistamines

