If a subject receives antihistamines only, the dose escalation can be continued. If symptoms during a build up day require antihistamines in multiple doses or in combination with other medications (except epinephrine), there should be a dose reduction by 1-2 doses with the next dose given in the CRC. If dose escalation fails or requires treatment after 2 more escalation attempts each spaced 2 to 4 weeks apart, the dose should be reduced to the last tolerated dose (must be at least 350 mg egg white solid to continue) and continued long term without further escalation.

Epinephrine

Any reaction (in clinic or at home) that requires 2 or more doses of epinephrine counts towards the stopping rules for the protocol. Further dose escalation would not occur in this individual and maintenance on the last tolerated dose (must be greater than 350 mg) would be maintained.

Clinic

If a single administration of epinephrine is required during in clinic escalation, the dose should be reduced by 2 doses, and the subject continued on that dose for 4 weeks. After 4 weeks at the reduced dose, an escalation attempt may be tried in clinic.

If a single administration of epinephrine is required a second consecutive time during this escalation attempt, the dose should be reduced by 2 doses, and the subject continues on that dose for 6-8 weeks. After 6-8 weeks at the reduced dose, an escalation attempt may be tried in clinic.

If a single administration of epinephrine is required a third consecutive time during this escalation attempt, the dose should be reduced by 2 doses (if the reduced dose is at least 350 mg egg white solid) and the subject continued on that dose as long-term maintenance without further escalation.

Home

If a single administration of epinephrine use occurs during dosing at home, this epinephrine use is not counted as one of the uses described above, unless severe anaphylaxis occurs at home. The subject should return to clinic for an observed dose prior to resuming any dosing at home. The investigator may or may not decide to dose reduce depending on the specific circumstances surrounding the reaction.

MAINTENANCE PHASE (PRE 1 YEAR 7444 MG EGG WHITE PROTEIN OFC PHASE)

This phase consists of the subject receiving the maximum achieved daily dose of either baked egg or egg white solid OIT (as described above) for at least 8 weeks at home. The subject will continue to follow an egg-restricted diet for the duration of the study.

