For any noted symptoms during the maintenance phase, the same general study dosing rules for the build-up phase will be followed. Dosing reductions during the maintenance phase will be determined by the investigator based on the circumstances surrounding the reaction and subsequent dosing reactions.

Both Treatment Groups:

One year 7444 mg egg white protein OFC (at the conclusion of the initial build-up and initial maintenance phase) - All subjects will undergo a 7444 mg egg white protein OFC at 52 weeks after reaching the maximum achieved daily dose for 8 weeks as described above. Even though subjects initially may not tolerate more than approximately 2 gm of baked egg protein or 350 mg of egg white solid, long-term administration of egg may result in the capacity to tolerate much higher doses, and indeed 80% of individuals on 300 mg of egg white solid maintenance therapy for 24 months were "protected" and passed a 10 gm OFC.³⁷

All subjects who did not reach the maximum maintenance dose of Egg OIT will resume build-up starting at their current maintenance dose and stopping at the maximum maintenance dose or earlier if symptoms prevent further build-up. The doses administered and parameters for build-up

in the post 1 year 7444 mg egg white protein OFC phase will be identical to those in build-up prior to the 1 year 7444 mg egg white protein OFC.

Long Term Maintenance:

The year 2 maintenance portion of the study is to determine if the Baked Egg and/or Egg OIT can induce the development of sustained unresponsiveness to egg. Subjects in the treatment arm will remain on a daily dose of Baked Egg or Egg OIT (or resume build-up to reach the maximum maintenance dose as described above at least 4 weeks prior to the 2 year 7444 mg egg white protein OFC).

Subjects on each arm of the study will be followed with visits at 4 months (Visit 05) and 8 months (Visit 06) after the 1 year 7444 mg egg white protein OFC. At these visits, serum for egg-specific IgE and IgG4 will be obtained (up to 10 mL). Subjects will be called monthly to assess for dosing compliance, symptoms and a targeted history.

Missed Baked Egg Doses:

Baked Egg subjects will be encouraged to take the daily baked egg dose. Missed doses will be monitored for compliance through daily dosing diaries.

Missed Egg OIT Doses at any Phase of the Study:

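### Egg OIT rules conflict for a child with aggressively treated stage 3 anaphylaxis: Section 6.4.2 keeps the child on maintenance, while the build-up algorithm discontinues dosing

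*Protocol*

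**What the plan says.** **Section 6.4.2 (reactions during build-up and maintenance).** "If severe anaphylaxis (stage 3 defined in Appendix 3) occurs at any time, dose escalation will stop and the dose will be reduced". The new dose is the last one tolerated, with a floor of 350 mg egg white solid. What follows is "the subject continued on that dose as long-term maintenance without further escalation". The treatment given does not enter the rule.

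**Section 6.4, build-up symptom algorithm.** A child with hypoxia, hypotension or altered mental status, again defined as stage 3 by Appendix 3, who "receives aggressive therapy at any time should be discussed with the Study Chair or Co-Chair and discontinued from active therapy".

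**Section 4.3.1 (criteria for premature termination).** "Any subject deemed to have severe symptoms and receives aggressive therapy at any time should be discontinued from further therapy". This sentence does not mention stage 3. A separate bullet on anaphylaxis with hypotension, neurological compromise or mechanical ventilation has a permissive lead-in: "Any subject may be prematurely terminated from additional allergen exposures, but maintained on longitudinal follow-up".

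**Section 6.4.2, epinephrine rules.** After a reaction needing two or more doses, escalation ends and "maintenance on the last tolerated dose (must be greater than 350 mg) would be maintained". Under the Home rule, a single dose given at home joins the in-clinic count only if the reaction was severe anaphylaxis, and the consequence in that count is dose reduction. Neither rule mentions discontinuation for stage 3.

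**Section 6.4, maintenance phase.** "For any noted symptoms during the maintenance phase, the same general study dosing rules for the build-up phase will be followed". Dose reductions there are left to the investigator.

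**The concern.** Two instructions in the same part of the protocol cover the same event, cite the same appendix and both apply at any time during dosing. One ends dosing; the other continues it as long-term maintenance. A site that follows Section 6.4.2 to the letter would resume daily allergen, given largely at home, to a child just treated for hypoxia, hypotension or neurological compromise. Another written rule removes that child from dosing. Whichever action the site takes departs from one written rule, so it is also unclear which choice counts as a protocol deviation. The main stake is the safety of a child on Egg OIT; the effect on the analysis is secondary.

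**Working it through.** **1. Triggers and actions side by side.**

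| Rule | Trigger | Action |
|---|---|---|
| 6.4 build-up algorithm | Stage 3 symptoms and aggressive therapy | Discuss with Chair or Co-Chair and discontinue |
| 4.3.1 sentence | Severe symptoms and aggressive therapy | Discontinue |
| 6.4.2 | Stage 3 anaphylaxis, any treatment | Stop escalation, reduce to last tolerated dose (at least 350 mg), continue long term |
| 6.4.2, two or more epinephrine doses | Any reaction needing them | Stop escalation, maintain on last tolerated dose (above 350 mg) |

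**2. Where they collide.** The first and third rows share cases when three things hold: the reaction is stage 3, aggressive therapy was given, and the last tolerated dose is at least 350 mg. Below that floor Section 6.4.2 does not permit continuation, so there is no clear conflict.

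**3. Is the overlap empty in practice?** No. Appendix 3 stage 3 means hypoxia, hypotension or neurological compromise. Section 6.4.2 directs that "for more severe symptoms, the subjects should receive epinephrine, antihistamines, and then the other medications as indicated", so stage 3 children will normally be treated, and some intensively. The protocol does not define aggressive therapy, so a site cannot tell from the text where the boundary lies.

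**4. Does the conflict stop at build-up?** No. The heading of Section 6.4.2 covers maintenance, and the maintenance text carries the build-up dosing rules forward.

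**5. Which doses are affected?** This depends on what last tolerated dose means. If it is exactly one step below the reacting dose, a reaction at 350 mg drops to 260 mg, below the floor, and the conflict starts at 450 mg. If a child who had been tolerating 350 mg reacts at home, the last tolerated dose could arguably be 350 mg itself. The protocol does not settle this. The build-up algorithm lists the last tolerated dose and a 1-2 step reduction as alternatives.

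**6. Effect on the primary endpoint.** Inputs: 96 randomized 1:1, so 48 per arm; design rates 40% and 70% (Section 9.3); a child who does not attempt the off-therapy challenge is a failure (SAP 3.3).
- One child: 1/48 = 2.1 percentage points at most.
- Design counts: 0.40 × 48 = 19.2, taken as 19; 0.70 × 48 = 33.6, taken as 34.
- Pearson chi-square without continuity correction, Egg OIT vs Baked Egg: 34/48 vs 19/48, p = 0.002. With one Egg OIT success lost, 33/48 vs 19/48, p = 0.004. With two lost, 32/48 vs 19/48, p = 0.008.

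One or two such children would not change the conclusion at the design rates.

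**The case against.** **The rules can be read together.** The algorithm carries an extra condition, aggressive therapy, and a specific rule ordinarily qualifies a general one. On that reading an aggressively treated child is discontinued, and any other stage 3 child is reduced and maintained. The second category is real: Appendix 3 makes an oxygen saturation of 92% or below stage 3 on its own. This is the most sensible reading, and the fix adopts it. But Section 6.4.2 contains no such condition, and its reduction is worded as mandatory while the algorithm uses the weaker *should*.

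**Safeguards exist.** The algorithm itself calls for discussion with the Chair or Co-Chair. The Chair is also available for dosing questions the protocol leaves unanswered, and investigators may discontinue dosing on their own judgment. Serious events are reported within 24 hours (Section 7.4.2). The DSMB may recommend withdrawing a participant (Section 7), and the sponsor, FDA and DSMB may suspend treatment (Section 7.4.2). These make harm less likely. None says which rule governs, and the unanswered-question clause does not fit a question answered twice.

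**Other text may settle it.** Exhibits 1 and 2 of Section 6 are not in the available text, so the point is limited to the written rules. Section 11.2 also shows that some children had finished before version 6.0, which limits how many an amendment can reach.

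**Stronger readings that the documents do not support.** A reader might infer that every stage 3 event must end Egg OIT. The algorithm requires aggressive therapy as well, and the 4.3.1 anaphylaxis bullet is permissive. A reader might infer that any epinephrine counts as aggressive therapy. Section 6.4.2 allows another escalation attempt after a single in-clinic dose, and the algorithm lets the physician re-dose after severe respiratory or gastrointestinal symptoms. A reader might also set the Baked Egg termination rule in Section 6.4.1 against Section 6.4.2 as like for like. Its trigger is narrower (hypotension, neurological compromise or mechanical ventilation) and does not name hypoxia alone.

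**Conclusion.** The inconsistency stands in a bounded form. For a child on Egg OIT with stage 3 anaphylaxis, aggressive therapy and a last tolerated dose of at least 350 mg, the protocol gives opposite instructions and does not say which prevails. Section 4.3.1 favors discontinuation. The conflict is one of wording, and a reasonable reader can resolve it, but a safety rule should not depend on that.

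The documents give no event count. Few events are expected: the earlier egg OIT trial described in Section 1.1 reported mild to moderate year-1 dosing symptoms, with 11,860 egg doses given, and Section 4.2 excludes children with prior egg anaphylaxis that led to hypotension, neurological compromise or mechanical ventilation. The effect on the primary comparison is immaterial, assuming one or two affected children at the design rates. The conclusion also assumes that Exhibits 1 and 2 do not already state a precedence. It should be fixed on safety grounds.

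**What to change.** 1. Keep the stop-escalation-and-reduce sentence in Section 6.4.2 for stage 3 events not treated aggressively. Deleting it would leave those events without that instruction. Insert before it, for example: *When stage 3 anaphylaxis to Egg OIT is treated with aggressive therapy, Egg OIT ends after consultation with the Chair or Co-Chair, and follow-up continues under Section 4.3.2. This takes precedence over every dose-reduction rule in Section 6.4.2.*
2. Add the same stage 3 exception to the two-or-more-epinephrine rule and to the Home rule.
3. Define aggressive therapy once, for stage 3 events only, with the threshold chosen by the sponsor. Do not set it at any single epinephrine dose for Section 4.3.1: that section is not limited to stage 3, and the definition would then contradict the rules that allow dosing to continue after other severe reactions or after one epinephrine dose.
4. Check Exhibits 1 and 2 for the same wording.
5. If the sponsor prefers to end Egg OIT after every stage 3 event, including isolated hypoxia, present that as a deliberate tightening, because it goes beyond the current text.

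Cost: a few sentences of amendment text, one definition and a memo to sites. No added visits, procedures or sample size.

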6.5 Oral Food Challenge Double-Blind Placebo Controlled

Investigators in the Consortium have utilized powdered egg white solid for oral food challenges at their respective institutions for more than 10 years. The egg white solid will be the bulk drug substance sent to each site by the central manufacturer. The subject will be off antihistamines for an appropriate length of time (5 half-lives of the antihistamine that is being used). Oral food challenges will be undertaken under direct medical supervision in a Clinical Research Center or food challenge area with emergency medications and staff immediately available and will follow established study procedures. Prior to the OFC, subjects will be assessed for an exacerbation of asthma as determined by active wheezing or a peak expiratory flow rate <80% of predicted. A uniform approach for food challenges will be used. Frequent assessments will be made for symptoms affecting the skin, gastrointestinal tract, and/or respiratory tract. Dose limiting symptoms, typically objective symptoms, indicate a positive reaction and termination of dosing.

6.6 Egg OFC

All egg OFCs conducted in the study are double-blind placebo controlled food challenges. All egg doses for OFCs are described in mg of protein. The OFC is performed by feeding gradually increasing amounts of the suspected food under physician observation.^{87,88} OFC is conducted as 2 challenges during a single day visit or over 2 days using placebo for 1 challenge and the study egg white protein for the other. If conducted in a single day, at least 2 hours must separate the first half of the challenge from the second half of the challenge. The challenge is performed so that neither the subject, nor the subject's caregiver nor the physician knows which challenge contains the egg white protein or the placebo. The initial OFC for eligibility will consist of administering egg white protein or placebo in gradually increasing doses at 15-30 minute intervals. Extra doses may be added if 1444 mg of protein is successfully consumed on the baseline challenge per standard of care at the investigators discretion. If more than 1444 mg of egg white protein is successfully consumed without dose limiting symptoms, the subject would not be eligible for the study. The doses for the initial egg OFC are 1, 3, 10, 30, 100, 300, and 1000 mg of egg white protein. The 1 year 7444 mg egg white protein OFC will be done while on therapy and is not followed by a repeat OFC or open feeding. The 2 year 7444 mg egg white protein OFC will be done on therapy to assess desensitization. In those who pass the desensitization challenge, a follow up 7444 mg egg white protein OFC off therapy will be done followed with an open feeding of a meal sized portion of egg 1 hour later, if this challenge is passed. Although these minimum standards have been used safely in the past, the investigator may use clinical judgment to increase the intervals between doses; or repeat lower doses, if there is a concern that a reaction may be developing. The doses for the 7444 mg egg white protein OFC are 1, 3, 10, 30, 100, 300, 1000, 3000, 3000 mg of egg white protein. Though many published challenges begin with 5 mg initial doses, the minimum dose for this study was chosen to be 1 mg according to additional recent recommendations and consensus.

6.7 Baked Egg OFC

The baked egg challenge conducted in this study will be a double-blind placebo controlled challenge. A uniform approach for baked egg challenges will be used.

A single baked food group will be used though the initial challenge will be a muffin product using a uniform SOP across all five participating centers. Recipes are included in the CoFAR7 MOP.

The doses will be distributed in 6 escalating doses of approximately 5%, 10%, 15%, 20%, 25% and 25% of the total 2 gm baked egg protein dose. A successful challenge is the consumption of a cumulative dose of 2 grams of the baked egg protein challenge without dose limiting symptoms.

6.8 Prick Skin Test

Subjects will have prick skin tests performed using study approved procedures for food and environmental allergens. While the subject is off antihistamines for an appropriate length of time (5 half-lives of the antihistamine that is being used), a skin test probe is pressed through a commercial extract of an allergen into the epidermis. Positive (histamine) and negative (saline-glycerin) controls are placed to establish that the response is not blocked and to determine if there is dermatographism, respectively.

6.9 Visit Windows

Dosing schedule should be adhered to strictly. Two days before, or 5 days after, a planned dosing visit is an acceptable window with continued daily dosing of the current dose level. Study visits will be completed approximately 7 days before or 7 days after the planned visit. Study visits for OFC should take place within 2 weeks of the scheduled visit. Monthly telephone contacts that occur between clinic visits will occur approximately 7 days before or 7 days after the planned contact.

6.10 Study Blinding Procedures

This study is not blinded.

7. Safety Monitoring

This section defines the types of adverse events that should be reported and outlines the procedures for appropriately collecting, grading, recording and reporting them. The investigator is responsible for the detection and documentation of events meeting the criteria and definition of an AE (Adverse Event) or SAE (Serious Adverse Event) as described in sections 7.2.1 and 7.2.2. All AEs and SAEs will be recorded in the source documents and on the appropriate electronic CRF(s). All data will be reviewed periodically by the DSMB, which may provide recommendations to DAIT/NIAID/NIH about withdrawing any participant and/or terminating the study because of safety concerns.

Information in this section complies with 21CFR 312; ICH Guideline E2A: Clinical Safety Data Management: Definitions and Standards for Expedited Reporting; and ICH Guideline E-6: Guidelines for Good Clinical Practice; and applies the standards set forth in the National Cancer Institute (NCI), Common Terminology Criteria for Adverse Events, Version 4.0 (May 28, 2009). This document is referred to herein as the "NCI - CTCAE Manual."

